4.6.5. Electrocardiograms

Treatment-emergent qualitative electrocardiogram (ECG) abnormalities are defined as qualitative abnormalities that first occurred after the first dose of study intervention. Qualitative abnormal ECGs will be recorded as AEs. A listing of qualitative ECGs may be produced.

4.6.6. Clinical Laboratory Evaluation

All laboratory data will be reported in SI units. Selected laboratory measures will also be reported using conventional units. Limits from the performing lab will be used to define low (L) and high (H). Descriptive summaries by treatment and by nominal visit will be provided for the baseline and postbaseline values, as well as the change from baseline values.

Observed and change from baseline values for each visit may be displayed in plots for participants who have both a baseline and at least 1 postbaseline planned measurement. Baseline will be the last non-missing observation prior to taking the first study drug. Unplanned measurements will be excluded from plots.

A shift table will be provided including unplanned measurements. The shift table will include the number and percentage of participants within each baseline category (low, normal, high, or missing) versus each postbaseline category (low, normal, high, or missing) by treatment. The proportion of participants shifted will be compared between treatments using Fisher's exact test.

For qualitative laboratory analytes, the number and percentage of participants with normal and abnormal values will be summarized by treatment.

A listing of abnormal findings will be created for laboratory analyte measurements, including qualitative measures. The listing will include participant identification, treatment group, laboratory collection date, study day, analyte name, and analyte finding.

Using the SAS, the MMRM model as described in Section 4.3.2 will be used for the analysis during the treatment period for the continuous measurements for selected lab tests. Alternatively, ANCOVA will be used if the MMRM model is not applicable due to unavailability of multiple postbaseline measurements.

Detailed analyses can be found in Appendix 7 (Section 6.7).

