9.3.5.1. Laboratory Measures and Vital Signs

Laboratory measures and vital signs will be summarized for each scheduled visit by

- actual measures at baseline and postbaseline
- change from baseline to postbaseline, or
- percent change from baseline to postbaseline.

The laboratory measures may be log transformed before statistical analyses, if deemed necessary. Continuous variables, as well as the change from baseline for these variables or other appropriate transformed variables, will be analyzed by MMRM models as described in Section 9.3.1.

The percentages of participants with treatment-emergent abnormal, high, or low measures, including laboratory and vital signs, will be summarized and compared between treatment groups using Fisher's exact test.

The analysis details will be provided in the SAP.

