(Treatmen t k vs. Reference Arm)	SE	$e^{\bar{Z}_{b}} \sqrt{e^{2\hat{\mu}_{\Delta Z,k}} \cdot \left(\widehat{SE}_{\Delta Z,k}\right)^2 + e^{2\hat{\mu}_{\Delta Z,R}} \cdot \left(\widehat{SE}_{\Delta Z,R}\right)}$	$\exp(\hat{\mu}_{\Delta Z, k \ vs \ R}) \cdot \widehat{SE}_{\Delta Z, k \ vs \ R} \times 100$
12)	P-value	NR	P∆Z,k vs R
	95% CI	Estimate $\pm \Phi^{-1} (1 - \frac{\alpha}{2}) * SE$	$(\left[\exp\left(L_{\Delta Z,k\ vs\ R}\right)-1\right]\times 100, \left[\exp\left(U_{\Delta Z,k\ vs\ R}\right)-1\right]\times 100)$

Abbreviation: CI = confidence interval; NR = not reported; SE = standard error.

In general, a time-averaged parameter will refer to the area under the curve (AUC) constructed using the trapezoidal rule, applied to the parameter according to the scheduled time, divided by the length of observation. For example, a time-averaged dependent variable for Days 30 to 180 will equal AUC/150, where AUC represents the AUC constructed by the trapezoidal rule.

Unless otherwise specified, baseline is defined as the last non-missing measurement recorded on or before the randomization visit, prior to first dose of intervention.

When considering treatment-emergent abnormal safety laboratory values and vital signs, baseline observation will start from the screening visit and end prior to, or at, the randomization visit, wherein all scheduled and unscheduled measurements will be included. The baseline for the treatment-emergent safety analysis will be the maximum/minimum from all measurements taken during the baseline period. For postbaseline measurements, all scheduled and unscheduled measurements in the analysis period will be included. The maximum/minimum from all measurements taken during the analysis period will be used in the treatment-emergent safety analysis. The end of Study EZCB participation for a participant will be the earliest of date of death, the date of withdrawal from further participation in the study, or the date of the safety follow-up visit (Visit 801). For participants considered to be lost to follow-up, end of Study EZCB participation will be the date participant is lost to follow-up as reported by the investigator. Participant data included in the database after the last date of Study EZCB participation (including the safety follow-up period) will be excluded from statistical analysis.

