Participants with elevated or low values meeting specified levels	Excludes analytes collected qualitatively. Definitions provided in Table 59 and 60 from FDA's Standard Safety Tables and Figures Integrated Guide will be used for the numerator ^b . Includes participants with at least 1 postbaseline measurement. For initial controlled analysis sets, maximum baseline is used for elevated assessments and minimum baseline is used for low assessments. For LY-treated analysis sets (all participants receiving at least 1 dose of LY3561774), participants randomly assigned to placebo or active comparator in the initial period, last baseline is used for any change calculations.	FAS
	For controlled analysis sets, statistical comparisons (using methods described in Section 4.3.2) will be included. See Table 24 from FDA's Standard Safety Tables and Figures Integrated Guide (FDA 2022).	
Listing of abnormal laboratory findings	Includes laboratory analytes collected quantitatively (high or low during postbaseline using Level 2 definitions) and qualitatively (abnormal during postbaseline).	FAS

Analysis Type	Analysis Details	Population/Analysis
		Set
	Includes participant identification, treatment group, laboratory analyte collection day (that is, days	
	from start of study intervention), analyte name, and analyte finding.	

Abbreviations: ANCOVA = analysis of covariance; FAS = full analysis set; MMRM = mixed model repeated measures; SD = standard deviation.

- a [PHUSE]. Safety Analytics Working Group. Analyses and displays associated with laboratory analyte measurements in phase 2-4 clinical trials and integrated submission documents update to recommendations. Accessed March 05, 2023. https://phuse.s3.eu-central-1.amazonaws.com/Deliverables/Safety+Analytics/WP068.pdf
- b [FDA] United States Food and Drug Administration. Standard safety tables and figures: integrated guide. August 2022. Accessed May 31, 2023. https://downloads.regulations.gov/FDA-2022-N-1961-0046/attachment_1.pdf

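### The laboratory shift test in SAP 4.6.6 does not define which moves count, so its p-value does not test for new laboratory abnormality

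*SAP*

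**What the plan says.** SAP 4.6.6 (Clinical Laboratory Evaluation) describes a shift table of "each baseline category (low, normal, high, or missing) versus each postbaseline category (low, normal, high, or missing) by treatment", including unplanned measurements. The next sentence gives the test: "The proportion of participants shifted will be compared between treatments using Fisher's exact test". The section does not say which cells make a participant shifted, whether direction matters, which postbaseline value (maximum, minimum or last) sets the category, or how the missing category enters the test.

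Protocol 9.3.5.1 asks a directional question: "The percentages of participants with treatment-emergent abnormal, high, or low measures, including laboratory and vital signs, will be summarized and compared between treatment groups", by Fisher's exact test, with details left to the SAP.

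The SAP prepares for that question in two other places.
- Section 4.1, on treatment-emergent laboratory values and vital signs: "The baseline for the treatment-emergent safety analysis will be the maximum/minimum from all measurements taken during the baseline period".
- Appendix 7 (Section 6.7), on participants with elevated or low values meeting specified levels: "maximum baseline is used for elevated assessments and minimum baseline is used for low assessments". Its test is given as: "For controlled analysis sets, statistical comparisons (using methods described in Section 4.3.2) will be included".

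Section 4.3.2 is the MMRM for log-transformed continuous data. SAP 4.9, which lists changes to the protocol-planned analyses, does not mention laboratory comparisons.

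**The concern.** A 4 x 4 table has 16 cells, 12 of them off the diagonal. Of those 12, four are new abnormality in one direction (normal or low to high, normal or high to low), two are improvements (high to normal, low to normal), and six involve the missing category. If shifted means any off-diagonal cell, the null hypothesis is an equal chance of changing category, which is not an equal chance of becoming abnormal.

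Two errors can follow. A drug that pushes normal values high and also slows the recovery of high values raises one component and lowers the other, so the between-arm difference shrinks. A drug that only normalises values produces a difference with no harm behind it.

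Both need participants who are abnormal at baseline, and entry allows for them: triglycerides must be 150 to 499 mg/dL, ALT is admitted up to 3 times ULN, and HbA1c is admitted below 8%. Hepatobiliary events are a named potential risk in Protocol 2.3.1.

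**Working it through.** **The plan's figures.** The documents give no power, event rate or detectable difference for this test. Arm sizes follow from Protocol 9.5: 175 x 2/7 = 50 for placebo, 400 mg and 800 mg, and 175 x 1/7 = 25 for 100 mg. The test level is 0.05, two-sided (SAP 4.1).

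**Assumed inputs.** No transition rate stands in the documents, so all those below are assumptions. For one analyte and one arm, let b be the share high at baseline, u the probability that a normal value becomes high, and r the probability that a high value becomes normal. Low and missing are ignored for simplicity. Then:
- worsening = (1 - b) x u
- improving = b x r
- shifted (literal reading) = (1 - b) x u + b x r

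Power is the sum, over all pairs of binomial counts, of their joint probability wherever the two-sided Fisher p-value is at most 0.05. Both tests use all randomised participants as denominator.

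**Harm cases**, 50 v 50, u = 5% placebo v 35% active:

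| b | r, placebo v active | Shifted | Worsening | Power, shifted | Power, worsening | Loss |
|---|---|---|---|---|---|---|
| 0% | not applicable | 5% v 35% | 5% v 35% | 97% | 97% | 0 points |
| 5% | 50% v 20% | 7.25% v 34.25% | 4.75% v 33.25% | 91% | 96% | 5 points |
| 10% | 50% v 20% | 9.5% v 33.5% | 4.5% v 31.5% | 80% | 94% | 14 points |
| 30% | 20% v 20% | 9.5% v 30.5% | 3.5% v 24.5% | 69% | 83% | 14 points |
| 30% | 50% v 50% | 18.5% v 39.5% | 3.5% v 24.5% | 57% | 83% | 26 points |
| 30% | 50% v 20% | 18.5% v 30.5% | 3.5% v 24.5% | 22% | 83% | 61 points |

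Worked example for the last row, placebo: 0.7 x 5% + 0.3 x 50% = 3.5% + 15% = 18.5%. Active: 0.7 x 35% + 0.3 x 20% = 24.5% + 6% = 30.5%. For the 100 mg arm (50 v 25) the same row gives 17% v 74%.

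A second set of rates (b = 30%, u = 10% v 35%, r = 60% v 20%) gives the same pattern: shifted 25.0% v 30.5%, power 6%, against 59% for worsening alone.

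**Benefit only**, 50 v 50, b = 50%, u = 5% in both arms, r = 30% v 80%. Shifted is 2.5% + 15% = 17.5% v 2.5% + 40% = 42.5%. The shift test rejects 73% of the time; a worsening-only test rejects about 0.1% of the time.

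**A single data set.** With 5 of 50 v 15 of 50 worsened, Fisher's p = 0.023. If 10 v 0 also improved, the shifted counts are 15 v 15 and p = 1.00.

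**At-risk denominator.** With b = 30%, 35 per arm start in range. Fisher's test of 5% v 35% at 35 v 35 has 87% power, against 83% for worsening over all 50 per arm. In this case the smaller denominator costs nothing.

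**The case against.** A reader might infer that a real laboratory harm could pass unseen in this trial, or that this is the only Fisher's test the SAP gives laboratory data. The documents support neither.
- SAP 4.1 has a general rule that other categorical outcomes are compared by Fisher's exact or Pearson's chi-square test, and it sets the maximum/minimum baseline for treatment-emergent laboratory values.
- Table EZCB.4.5 tabulates the liver analytes against upper thresholds and adds drug-induced liver injury screening displays.
- Appendix 7 plans elevated/low analyses, and changes in minimum and maximum values with p-values.
- The shift table prints every cell by treatment, so direction is visible beside the p-value.

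It is also fair to say that counting every off-diagonal cell is only one reading, because the SAP leaves shifted undefined. The large losses depend on chosen rates. The entry limits for ALT and HbA1c are ceilings and do not show that many participants start abnormal. Triglycerides are raised by design, but they are an efficacy endpoint with their own MMRM, so a triglyceride improvement would hardly be taken for harm. If the postbaseline maximum sets the category, recovery requires every later value to be in range, and recovery rates of 50% to 80% become harder to justify.

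All of that stands, and it limits the point to one p-value. It does not remove it. SAP 4.6.6 states no treatment-emergent high/low laboratory comparison for the general rule to act on. Table EZCB.4.5 covers liver analytes only and names no test. The minimum/maximum analysis compares mean changes, not the incidence of new abnormality. The Appendix 7 elevated/low comparison is expressly sent to an MMRM section, which cannot compare proportions.

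**Conclusion.** The point holds in this limited form. The Fisher's test in SAP 4.6.6 has no defined outcome. On its literal reading it mixes improvement, deterioration and missingness, and it cannot be read as a test of new laboratory abnormality. The comparison promised in Protocol 9.3.5.1 is not carried into SAP 4.6.6, and SAP 4.9 does not record its absence. Harm could be masked in this one comparison, not in the laboratory evaluation as a whole.

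The size depends on the analyte. The loss of power is nil where nobody is abnormal at baseline, 14 points with 10% high and reduced recovery, and 61 points with 30% high and reduced recovery. The 73% rejection rate under pure benefit assumes half the participants high at baseline and 30% v 80% normalising. All of these rates are assumptions, as is the literal reading of shifted. The primary result is unaffected, this is Phase 2 safety screening without multiplicity control, and no decision rule is tied to this p-value. It is a cheap improvement of minor to moderate severity.

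**What to change.** Replace the Fisher sentence in SAP 4.6.6 with two Fisher's exact tests per quantitative analyte, each dose against placebo, using the baseline rule already in SAP 4.1:
- **Treatment-emergent high:** baseline maximum at or below the upper limit, and any postbaseline value above it.
- **Treatment-emergent low:** baseline minimum at or above the lower limit, and any postbaseline value below it.

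The denominator for each is the participants at risk who have a baseline and at least one postbaseline value. Keep the shift table as a descriptive display without a p-value, state which postbaseline value sets its category, and leave the missing category outside any test. In Appendix 7, change the method for the elevated/low comparison from Section 4.3.2 to Fisher's exact test.

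The cost is SAP wording and a standard table; no new data are needed. The downside is two tests per analyte instead of one, and at-risk denominators smaller than the full arm.

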4.6.7. Additional Safety Assessments

4.6.7.1. Hepatic Safety

4.6.7.1.1. Hepatic Fat Fraction

The endpoint labeled "percent and absolute change from baseline for MRI hepatic fat fraction at Day 180," will be analyzed using the SAS.

ANCOVA will be used for the analysis of both percent and absolute change.

4.6.7.1.2. Hepatic Disorders

The counts and percentages of participants with TE, potentially drug-related hepatic disorders, will be summarized by treatment using the MedDRA PTs. Detailed search criteria can be found in Appendix 6 (Section 6.6)

4.6.7.1.3. Liver enzymes

Hepatic labs include alanine aminotransferase (ALT), aspartate aminotransferase (AST), total bilirubin (TBL), direct bilirubin (DBL), serum alkaline phosphatase (ALP), international normalized ratio (INR), and gamma-glutamyltransferase (GGT). When criteria are met for hepatic evaluations, investigators will conduct close monitoring of hepatic symptoms and liver tests, perform a comprehensive evaluation for alternative causes of abnormal liver tests, and complete follow-up hepatic safety electronic case report forms (eCRFs).

Table EZCB.4.5 describes the planned summary tables related to hepatic safety.

Table EZCB.4.5 Summary Tables and Figures Related to Hepatic Safety

Analysis	Population or Analysis Set
Abnormal Postbaseline Categories – Hepatic Safety Parameters ALT The number and percentage of participants with a measurement greater than or equal to 1X, 3X, 5X, 10X, and 20X the performing lab ULN during the treatment period for all participants with a postbaseline value. AST The number and percentage of participants with a measurement greater than or equal to 1X, 3X, 5X, 10X, and 20X the performing lab ULN during the treatment period for all participants with a postbaseline value. ALP The number and percentage of participants with a measurement greater than or equal to 2X and 3X the performing lab ULN during the treatment period will be summarized for all participants with a postbaseline. TBL The number and percentage of participants with a measurement greater than or equal to 2X, 5X, and 8X the performing lab ULN during the treatment period will be summarized for all participants with a postbaseline value. DBL The number and percentage of participants with a measurement greater than or equal to 2X and 5X the performing lab ULN during the treatment period will be summarized for all participants with a postbaseline value. GGT The number and percentage of participants with a measurement greater than or equal to 2X the performing lab ULN during the treatment period will be summarized for all participants with a postbaseline value.	SAS
Hepatocellular Drug-Induced Liver Injury Screening Plot (TBL vs ALT or AST)	SAS
Hepatocellular Drug-Induced Liver Injury Screening Table	SAS
Cholestatic Drug-Induced Liver Injury Screening Plot (TBL vs ALP)	SAS
Cholestatic Drug-Induced Liver Injury Screening Table	SAS
Participant profiles will be created for participants meeting criteria for a comprehensive hepatic evaluation (as defined in the protocol).	SAS

Analysis	Population or Analysis Set
Participant profiles will include demographics, disposition, information collected on the hepatic safety CRFs (where applicable) and a display of study drug exposure, adverse events, medications, blood pressure, heart rate, and the liver -related measurements over time.	

Abbreviations: 1X = one time the ULN; 2X = two times the ULN; 3X = three times the ULN; 4X = four times the ULN; 5X = five times the ULN; 10X = ten times the ULN; 20X = twenty times the ULN; ALP = alkaline phosphatase; ALT = alanine aminotransferase; AST = aspartate aminotransferase; CRF = case report form; DBL = direct bilirubin; FAS = full analysis set; GGT = gamma-glutamyl transferase; TBL = total bilirubin; ULN = upper limit of normal.

Planned and unplanned measurements will be included in the analyses listed in Table EZCB.4.5. The measurements do not need to be taken at the same blood draw. The maximum baseline will be the maximum non-missing observation in the baseline period. The maximum value will be the maximum non-missing value from the postbaseline period.

The primary purpose of the screening plots is to identify participants whose data warrant further review. For these plots, symbols will be used to indicate the randomized treatment.

For individual participants of interest, participant profiles will be reviewed. This review will include which treatment the participant was taking over time, the changes in hepatic labs over time, and the temporal association with potential causes. The review of participant profiles will also include the identification of any potential Hy's law case or potential cholestatic liver injury case that may have been missed by focusing only on the maximum values when determining 30-day time associations.

4.6.7.1.4. Gallbladder and biliary tract disorders

The counts and percentages of participants with treatment-emergent, potentially drug-related gallbladder and biliary tract disorders will be summarized by treatment using the MedDRA PTs. Detailed search criteria can be found in Appendix 6 (Section 6.6).

4.6.7.2. Hypersensitivity Events

Hypersensitivity reactions and related information reported in the eCRF will be listed and summarized by treatment.

Two main analyses will be performed:

- Potential Immediate Hypersensitivity: analysis of TEAEs occurring from the start of study drug administration up to 24 hours after the end of study drug administration. For events without the hypersensitivity eCRF, only date (no time) information is collected, and any events occurring on the same date as the study drug injection date will be included.
- Potential Non-Immediate Hypersensitivity: analysis of TEAEs occurring more than 24 hours after the end of study drug administration but prior to subsequent study drug administration

Summaries of all potential hypersensitivity reactions will be generated by PT with decreasing frequency by treatment. The AE database will be searched using predefined Standardized MedDRA Queries (SMQs) to identify events consistent with hypersensitivity events. Detailed search criteria can be found in Appendix 6 (Section 6.6).

4.6.7.3. Injection Site Reactions

Injection site reactions, incidence, and related information reported in the eCRF will be summarized by treatment. Information to be summarized includes the timing of the reaction relative to study drug administration and characteristics of the injection site reaction. Such characteristics include erythema, induration, pain, pruritus, and edema.

Potential injection site reactions will be searched by predefined MedDRA High Level Terms (HLTs) of injection site reactions, administration site reactions, and infusion-related reactions.

Detailed searching criteria for injection site reaction events can be found in Appendix 6 (Section 6.6). The PT will be used for the summary by treatment within each HLT category.

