6.1. Study Intervention(s) Administered

Each participant will receive either placebo or LY3561774 via subcutaneous injection.

Intervention Name	LY3561774	Placebo
IMP and NIMP	IMP	IMP
Authorized as defined by EU Clinical Trial Regulation	No	No
Use	Experimental	Placebo-control
Dose Form	Solution	Solution
Unit Dose Strength(s)	200 mg/mL	Not applicable
Dosage Level(s)	100 mg 400 mg 800 mg	Not applicable
Route of Administration	Subcutaneous injection	Subcutaneous injection
Sourcing	Provided centrally by the sponsor	Commercially available 0.9% sodium chloride solution.
Labeling	Study intervention will be labeled as appropriate for country requirements.	

Abbreviations: IMP = investigational medicinal product; NIMP = non-investigational medicinal product.

This table describes the number of injections for the different intervention dose groups.

Intervention group	Number of injections
100 mg or matched placebo participants	1 injection
400 mg or matched placebo participants	1 injection
800 mg or matched placebo participants	2 injections

Location of subcutaneous injections

All SC injections will be administered into the SC tissue of the abdominal wall, 5 to 10 cm from the umbilicus.

If multiple injections are needed, they will be performed in quick succession and each injection should be delivered into separate quadrants in the anterior abdominal wall.

Record the package number and location of each injection.

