6.3. Measures to Minimize Bias: Randomization and Blinding

Randomization

All participants will be centrally assigned to randomized study intervention using an IWRS. Before the study is initiated, the log in information and directions for the IWRS will be provided to each site.

Participants will be randomly assigned in a 2:1:2:2 ratio to placebo: LY3561774 100 mg:400 mg:800 mg. Placebo participants will be randomly assigned so that each dose cohort will have a matching placebo cohort that receives the same dose volume to maintain the study blind.

Participants will be stratified according to the Visit 1 TG level of <250 mg/dL and \geq 250 mg/dL.

Maintaining blinding

Investigators will remain blinded to each participant's assigned study intervention within each dose group, throughout the course of the study. To maintain this blind, an otherwise unblinded third party will be responsible for the receiving, registering, preparing, and administering of all study intervention. Although the participant and the investigator will know the injection volume, they will not know whether the participant is receiving LY3561774 or placebo. To mitigate the risk of unblinding due to color difference between IMPs, site will be trained on additional operational procedures. Unblinded personnel who administer IMP to participants at Visit 2 will have no other interaction, role, or responsibilities other than receiving, registering, preparing, and administering IMP at Visit 6 in the trial. Participants should be instructed to look away during IMP administration.

Emergency unblinding

The IWRS will be programmed with blind-breaking instructions. In case of an emergency, the investigator has the sole responsibility for determining if unblinding of a participant's intervention assignment is warranted. Participant safety must always be the first consideration in making such a determination.

If a participant's intervention assignment is unblinded, the sponsor must be notified immediately within 24 hours of this occurrence. The date and reason that the blind was broken must be recorded.

Discontinuation from the study in case of unblinding

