9.5. Sample Size Determination

The sample size calculation is based on the primary efficacy estimand and its endpoint, percent change from baseline at Day 180 in ApoB.

Approximately 175 participants will be randomly assigned in a 2:1:2:2 ratio to placebo: LY3561774 100 mg:400 mg:800 mg. Assuming a 20% dropout rate, this results in approximately 20 completers for 100 mg group and 40 completers per arm for the rest of the groups.

Assuming a standard deviation of 15%, and a 2-sided alpha level of 0.05, the completers for each treatment arms will provide >99% power to detect a treatment difference of -30% for the primary endpoint.

10. Supporting Documentation and Operational Considerations

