4.1. General Considerations

Statistical analysis of this study will be the responsibility of Eli Lilly and Company (Lilly) or its designee. Some analyses and summaries described in this analysis plan may not be conducted if not warranted by data (for example, too few events to justify conducting an analysis). Additional exploratory analyses of the data may be conducted as deemed appropriate.

Unless otherwise noted, all tests of treatment effects will be conducted at a 2-sided alpha level of 0.05, and confidence intervals (CIs) will be calculated at 95%, 2-sided. All tests of interactions between treatment groups and other factors will be conducted at a 2-sided alpha level of 0.10.

Unless stated otherwise, statistical summaries and analyses will be conducted based on the planned randomized treatment groups: placebo, LY 100 mg, LY 400 mg, and LY 800 mg.

The primary estimand (a precise definition of the treatment effect to be estimated) of interest in comparing the efficacy of LY3561774 doses with placebo is the efficacy estimand (Section 1.1). The primary efficacy assessment, guided by the efficacy estimand, will be conducted using the efficacy analysis set (EAS) (Section 3). Subjects who received only the first dose of LY3561774 will be considered "on-treatment" during Day 1 to Day 90, whereas subjects who received both doses will be considered "on-treatment" during the entire treatment and assessment period.

Unless otherwise specified, safety assessments will be guided by an estimand comparing the safety of LY3561774 doses with placebo, irrespective of adherence to the study intervention. Thus, safety analyses will be conducted using the safety analysis set (SAS) (Section 3).

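### Injection-site reactions are set against one pooled placebo group, although 800 mg and its matched placebo receive two injections per dosing visit and every other group receives one

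*SAP*

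**What the plan says.** Protocol 6.1 tabulates injections per dosing visit: one for 100 mg, one for 400 mg, and two for the row labelled "800 mg or matched placebo participants". Each row includes the matched placebo. Dosing takes place twice (Protocol 4.1).

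Protocol 6.3 builds the placebo arm so that "each dose cohort will have a matching placebo cohort that receives the same dose volume to maintain the study blind". SAP 1.2 repeats this.

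The analysis does not carry that structure forward. SAP 4.1 sets the default groups as "planned randomized treatment groups: placebo, LY 100 mg, LY 400 mg, and LY 800 mg" and limits statistical comparisons to LY3561774 doses against placebo. For local reactions, SAP 4.6.7.3 says "Injection site reactions, incidence, and related information reported in the eCRF will be summarized by treatment". Neither that section nor SAP Appendix 6 departs from the default: there is no split by number of injections or matched cohort, and no rate per injection.

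SAP 4.6.7.3 names no test. Testing comes from the general rules: SAP 4.6.2 applies comparisons to treatment-emergent events by system organ class and preferred term, and Protocol 9.3.5 specifies Fisher's exact test.

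**The concern.** A local reaction can occur at each needle site, so the number of injections is part of the exposure. The pooled placebo group is a mixture of one- and two-injection participants and matches no active dose on this count. If the drug had no local effect at all, 800 mg would still be expected to show more participants with a reaction than placebo, and 100 and 400 mg fewer.

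Protocol 2.3.1 names injection-site reactions among the potential risks, and Protocol 2.1 says the study will inform dose decisions. The bias could suggest a local-tolerability problem at 800 mg that comes from the second needle, and could partly hide a real one at the lower doses. The design already contains the right controls; the analysis does not use them.

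**Working it through.** **The plan's own figure.** The only design calculation is for ApoB. Protocol 9.5: "Approximately 175 participants will be randomly assigned in a 2:1:2:2 ratio to placebo: LY3561774 100 mg:400 mg:800 mg". So placebo, 400 mg and 800 mg have 175 × 2/7 = 50 each, and 100 mg has 175/7 = 25. With 20% dropout these become 40 and 20 completers, as stated. For 40 against 20 completers, a difference of 30 and SD 15, the standardised difference is 30 / (15 × √(1/40 + 1/20)) = 7.3. Power is above 99.99%, so the stated >99% reproduces. It supplies the arm sizes below and has no other bearing here. No calculation is given for injection-site reactions.

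**Assumptions not in the documents**
- Reaction probability per injection, p: 3-10%, identical for drug and placebo.
- Share of the 50 placebo participants receiving two injections, w: one third (cohorts of about equal size, 16-17 people) to 40% (10:20:20, in proportion to the doses, 20 people).
- Both dosing visits completed, so 2 injections in total for one-injection participants and 4 for two-injection participants.
- Within-person correlation of reactions, ρ: 0, 0.3 or 0.5.

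**Mean injections per visit.** Pooled placebo has 1 + w, that is 1.33 to 1.40. The 800 mg group has exactly 2; 100 and 400 mg have exactly 1.

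**Expected incidence with no drug effect.** Under independence, the probability of at least one reaction in n injections is 1 − (1 − p)^n. With correlation, a beta-binomial gives 1 − ∏(b + i)/(a + b + i) for i = 0 to n − 1, where a = p(1 − ρ)/ρ and b = (1 − p)(1 − ρ)/ρ. Pooled placebo is (1 − w) × P(2 injections) + w × P(4 injections).

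Example, p = 5% and ρ = 0: one-injection groups 1 − 0.95² = 9.8%; 800 mg 1 − 0.95⁴ = 18.5%; pooled placebo 12.7% (w = 1/3) to 13.3% (w = 40%).

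Example, p = 5% and ρ = 0.3 (b = 2.217, a + b = 2.333): one-injection groups 8.3%, 800 mg 12.7%, pooled placebo 9.8-10.1%.

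Spurious difference from pooled placebo, in percentage points (range over w):

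| p | ρ | 800 mg | 100 and 400 mg |
|---|---|---|---|
| 3% | 0 | +3.3 to +3.7 | −1.9 to −2.2 |
| 5% | 0 | +5.3 to +5.9 | −2.9 to −3.5 |
| 10% | 0 | +9.2 to +10.3 | −5.1 to −6.2 |
| 3% | 0.3 | +1.7 to +1.8 | −0.9 to −1.1 |
| 5% | 0.3 | +2.7 to +2.9 | −1.5 to −1.8 |
| 10% | 0.3 | +4.8 to +5.3 | −2.7 to −3.2 |
| 3% | 0.5 | +1.0 to +1.1 | −0.6 to −0.7 |
| 5% | 0.5 | +1.6 to +1.8 | −0.9 to −1.1 |
| 10% | 0.5 | +2.9 to +3.3 | −1.6 to −2.0 |

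**Effect on a test.** By exact enumeration under independence, with 16 or 20 of the 50 placebo participants on two injections, Fisher's test of 800 mg against pooled placebo for any reaction rejects with probability 2.1-2.3% at p = 2%, 6.4-7.6% at p = 5% and 12.3-15.4% at p = 10%. Against two-injection placebo it stays below 4% throughout. These rates are for a composite of any reaction. The plan tests individual preferred terms, which are rarer, and correlation would shrink the bias behind these rates.

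**Cost of matching.** Standard error of the 800 mg contrast relative to the pooled one, for equal outcome variance: √(1/50 + 1/20) / √(1/50 + 1/50) = 1.32 with 20 controls, and 1.44 with 16. For 100 and 400 mg against all one-injection placebo (30-34 people), the ratio is 1.08 to 1.16.

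**The case against.** **The injection-site section only summarises.** This is correct, and the section alone does not support saying that reactions are formally compared there. The test enters through SAP 4.1 and 4.6.2 and Protocol 9.3.5, at preferred-term level. A pooled descriptive table carries the same distortion.

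**Independence is generous.** Protocol 6.1 has multiple injections given in quick succession into the same abdominal wall, and the same person is dosed again at about Day 90. Correlated reactions are plausible, and they roughly halve the excess at ρ = 0.3. The bias would vanish only if a person's injections always reacted together. This objection stands as to size, not direction.

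**A reader might infer a spurious dose-response gradient.** The documents do not support that. The 100 and 400 mg groups both get one injection, so injection number produces a single step at 800 mg. SAP 4.1 does not plan comparisons among active doses unless otherwise specified. Protocol 2.2 reports no apparent relationship of reactions to dose in Phase 1 Parts A and B, although it does not give the number of injections.

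**The data will exist anyway.** Protocol 8.3.4 provides a dedicated case report form for these reactions, Protocol 6.1 records package number and location for each injection, and SAP 4.1 allows additional exploratory analyses. Nothing is lost for good, but permission to do an analysis is not a plan to do it.

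**Conclusion.** The point holds as a low-cost improvement. As written, the plan gives every active dose a placebo control mismatched on number of injections, for an outcome that depends on that number and is a named potential risk. With no drug effect the comparison is biased upward at 800 mg and downward at 100 and 400 mg.

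Over p = 3-10%, the 800 mg excess is about 3 to 10 points under independence and about 1 to 5 points with a correlation of 0.3-0.5. The deficit in the one-injection groups is about 2 to 6 points under independence and smaller with correlation. The reaction probability, the placebo split and the correlation are all assumptions. At low reaction rates the harm is a distorted estimate, not an inflated false-positive rate.

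A reader might also infer that matching would separate injection number from dose altogether. It would not. It corrects the placebo comparison only; among the active doses, number and volume of injections stay tied to dose by design. No efficacy conclusion is affected.

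**What to change.** In SAP 4.6.7.3, add an injection-site reaction table that compares 800 mg with two-injection placebo, and 100 mg and 400 mg with one-injection placebo. An analysis stratified by number of injections would serve equally well. Report reactions per injection alongside, and keep the pooled table as a supplement.

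The cost is one extra table and wider intervals. The two-injection placebo cohort would be about 16-20 people, which raises the standard error of the 800 mg contrast about 1.3 to 1.4 times. Merging the 100 and 400 mg placebo cohorts matches injection number but not volume: at the stated 200 mg/mL those doses correspond to 0.5 mL and 2 mL. A table footnote should say so. Randomisation, dosing, sample size and the primary analysis need no change.
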